9.4.4 Vital Signs

Part A and Part B

For the treatment-emergent vital signs measurements, the observed values and change from baseline values will be summarized at each visit. The following vital signs parameters will be summarized: systolic and diastolic blood pressure (mm Hg), body temperature (°C), pulse rate (breaths per minute), and respiratory rate (breaths per minute).

The number and percentage of subjects meeting at least 1 threshold analysis criterion for selected parameters during the TE period will be summarized. The threshold analysis criteria are provided in [Appendix E](#).

In addition, a listing containing individual subject vital sign values will be provided. This listing will include data from both scheduled and unscheduled visits.

Part B Only

The number and percentage of subjects meeting at least 1 threshold analysis criterion at each visit will be summarized for blood pressure (systolic and diastolic). The threshold analysis criteria are provided in [Appendix E](#).

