- In the derivation of maximum and minimum values during TE periods, and maximum and minimum change from baseline values during TE periods for safety analyses
- In individual subject data listings as appropriate

Visit windowing rules: For analysis specified in Sections 9.2, 9.3, and 9.4, the analysis visit windows for protocol-defined visits are provided in [Appendix A](#).

Incomplete/missing data will not be imputed, unless specified otherwise.

Outliers: No formal statistical analyses will be performed to detect or remedy the presence of statistical outliers, unless specified otherwise.

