9.4.2 Clinical Laboratory

Part A and Part B

For the treatment-emergent laboratory assessments, the observed values and change from baseline values of the continuous hematology, coagulation and chemistry results will be summarized in SI units at each visit.

The number and percentage of subjects meeting at least 1 threshold analysis criterion event for selected parameters during the TE period will be summarized. The threshold analysis criterion shift from baseline will also be summarized for selected laboratory parameters. The threshold analysis criteria are provided in [Appendix E](#).

Results of urinalysis and the positive urine/serum pregnancy test will be listed in individual subject data listings only. For positive serum pregnancy listing, subjects with serum HCG which are abnormal will be selected.

In addition, a listing containing individual subject hematology, chemistry, and coagulation values will be provided. This listing will include data from both scheduled and unscheduled visits.

Part B Only

For selected LFT laboratory tests (alanine transaminase [ALT], aspartate transaminase [AST], alkaline phosphatase [ALP], and total bilirubin), a scatter plot of the maximum treatment-emergent value versus the baseline value corresponding to \times ULN (upper limit of normal) will be presented. Further, a scatter plot of the maximum treatment-emergent value of ALT and AST, separately, versus the maximum treatment-emergent value of total bilirubin corresponding to \times ULN will also be presented.

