9.4.5 Pulse Oximetry

Part A and Part B

For the treatment-emergent pulse oximetry measurements, a summary of observed values and change from baseline values will be provided at each visit for the percent of oxygen saturation.

The number and percentage of subjects with shift change from baseline (normal/missing and low according to the reference range) to the lowest percent of oxygen saturation during the TE period will be summarized. The reference range for normal oxygen saturation is specified as >95%, and ≤95% for low oxygen saturation.

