AST and Total Bilirubin	AST>3xULN and TBILI>2xULN	FDA DILI Guidance Jul 2009.
(ALT or AST) and Total Bilirubin	(ALT>3xULN or AST>3xULN) and TBILI>2xULN	FDA DILI Guidance Jul 2009.
GGT	>ULN - ≤2.5xULN >2.5x - ≤5xULN >5x - ≤20xULN >20xULN	CTCAE grade 1-4
Clinical Chemistry (NON-LFT)		
Albumin	<LLN - ≥30 g/L <30 - ≥20 g/L <20 g/L	CTCAE grade 1-3
Amylase	>ULN - ≤1.5xULN >1.5x - ≤2xULN >2x - ≤5xULN >5xULN	Criteria based upon CTCAE
Creatinine	>ULN - ≤1.5xULN >1.5x - ≤3xULN >3x - ≤6xULN >6xULN	CTCAE grades 1-4
Lipase	>ULN - ≤1.5xULN >1.5x - ≤2xULN >2x - ≤5xULN >5xULN	Criteria based upon CTCAE
Total protein	<LLN >ULN	No CTCAE
Creatine kinase	>ULN - ≤2.5xULN >2.5x - ≤5xULN >5x - ≤10xULN >10xULN	CTCAE grades 1-4
Hematology		
Hemoglobin	Hgb decreased (anemia) <LLN - ≥100 g/L <100 - ≥80 g/L <80 g/L Hgb increased >ULN - ≤20 g/L above ULN >20 g/L above ULN - ≤40 g/L above ULN >40 g/L above ULN	CTCAE grade 1-3 CTCAE grade 1-3

Table 12-4 Threshold Analysis Criteria for Laboratory Tests (as applicable)

Parameter	Threshold Analysis	Comments
Platelets	Platelet decreased <LLN - $\geq 75 \times 10^9 /L$ <75 - $\geq 50 \times 10^9 /L$ <50 - $\geq 25 \times 10^9 /L$ <25 $\times 10^9 /L$	CTCAE grade 1-4
	Platelet increased >ULN	No CTCAE available
Reticulocytes/Erythrocytes (%)	<LLN >ULN	No CTCAE
Coagulation		
Activated partial thromboplastin time (PTT)	>ULN - $\leq 1.5 \times ULN$ >1.5 - $\leq 2.5 \times ULN$ >2.5 $\times ULN$	CTCAE grade 1-3
Prothrombin time (PT) International Normalized Ratio (INR)	>ULN - $\leq 1.5 \times ULN$ >1.5 - $\leq 2.5 \times ULN$ >2.5 $\times ULN$	CTCAE grade 1-3

Table 12-5 Threshold Analysis Criteria for ECGs

Parameter	Threshold Analysis	Comments
HR	Bradycardia ≤ 50 bpm	
	Tachycardia ≥ 140 bpm	
PR	≥ 220 ms and increase from baseline ≥ 20 ms	
QRS	≥ 120 ms	
QTc	Absolute values (ms) >450 ms (Male); >470 ms (Female) ≥ 500 ms	To be applied to any kind of QT correction formula.
	Increase from baseline Increase from baseline 30-60 ms Increase from baseline >60 ms	

Table 12-6 Threshold Analysis Criteria for Vital Signs

Parameter	Threshold Analysis	Comments
SBP	>120 mmHg	
	<70 mmHg	
DBP	>80 mmHg	
	<50 mmHg	

Table 12-6 Threshold Analysis Criteria for Vital Signs

Parameter	Threshold Analysis	Comments
Weight	Weight gain ≥5% increase from baseline	
	Weight loss ≥5% decrease from baseline

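### The blood-pressure threshold tally in SAP 9.4.4 does not separate readings already beyond a limit before dosing from new ones, and no blood-pressure shift table is planned

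*SAP*

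**What the plan says.** SAP 9.4.4, for both Parts: "The number and percentage of subjects meeting at least 1 threshold analysis criterion for selected parameters during the TE period will be summarized". The blood-pressure rows of Table 12-6 (Appendix E) are bare values: SBP >120 or <70 mmHg, DBP >80 or <50 mmHg. None refers to baseline or asks for a repeat reading. Neither SAP 9.4.4 nor protocol 12.3.4.4 plans a shift table for vital signs.

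Elsewhere the SAP does bring baseline in:
- Laboratory tests, 9.4.2: "The threshold analysis criterion shift from baseline will also be summarized for selected laboratory parameters".
- Oxygen saturation, 9.4.5: "The number and percentage of subjects with shift change from baseline" to the lowest value in the treatment-emergent (TE) period.
- ECG, Table 12-5: the PR row is worded "ms and increase from baseline", and QTc has a category "Increase from baseline >60 ms".
- Weight, Table 12-6: a percentage change from baseline.

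SAP 9.4.4 also plans observed values and change from baseline by visit, a listing of individual values from scheduled and unscheduled visits and, in Part B only, the number of children meeting a blood-pressure threshold at each visit. Under SAP 9.1, unscheduled readings count "In the derivation of maximum and minimum values during TE periods".

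**The concern.** A child whose pressure was beyond a limit before dosing, and who crosses it again once on treatment, adds one to the tally exactly as a child who crosses it for the first time on drug. No eligibility criterion names a blood-pressure limit, so such children can be enrolled. The tally also takes the worst of six scheduled post-baseline visits plus any unscheduled readings, with no baseline figure beside it.

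Vital signs are a named part of the Part B primary endpoint, every child is treated, and safety is described without testing. A reader of this table has only baseline to judge it against. Change-from-baseline summaries do not show who crossed a limit, and counts per visit do not follow individual children. The point holds wherever the limits are set.

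**Working it through.** **The plan's own figure.** The documents give no figure for blood-pressure excursions. The only Part B sample-size figure is SAP Table 7-2, the chance of at least one subject with an AE, 1 − (1 − θ)^n. It reproduces: for n = 45, 1 − 0.95^45 = 90.06% and 1 − 0.90^45 = 99.13%; for n = 50, 92.31% and 99.48%. It does not bear on the threshold tally.

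**Inputs from the documents.** Six scheduled post-baseline vital-sign visits in the Part B treatment period: Day 15 and Weeks 4, 8, 12, 16 and 24 (protocol Table 3-4, SAP Table 12-2). About 56 children enrolled and 45 completing (SAP 7.2).

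**Assumptions.** No drug effect. A share q of readings lies beyond one given limit at any visit, with q from 1% to 10%. Readings are normal, with equal correlation ρ between any two readings in a child, ρ from 0.3 to 0.7. There is one baseline reading. All results are for one limit.

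**Formulas.** Let c = Φ⁻¹(1 − q), let B be a standard normal child effect, and let F(B) = Φ((c − √ρ·B)/√(1 − ρ)) be that child's chance that one reading stays within the limit.
- Flagged at least once in six visits: 1 − E[F⁶].
- Flagged and not beyond the limit at baseline: (1 − q) − E[F⁷].
- Flagged and already beyond at baseline: the difference of the two.

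**Central case, q = 5%, ρ = 0.5,** by numerical integration: E[F⁶] = 0.8141 and E[F⁷] = 0.7967.
- Flagged: 1 − 0.8141 = 18.6%, or 10.4 of 56 (8.4 of 45).
- New: 0.95 − 0.7967 = 15.3%, or 8.6 of 56.
- Already beyond: 18.6% − 15.3% = 3.3%, or 1.8 of 56. This is about 17.5% of those flagged.

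| q | Flagged over six visits, ρ = 0.5 (range for ρ 0.3–0.7) | Of 56 | Share already beyond at baseline, ρ = 0.5 (range) | New-onset, % of all children, ρ = 0.5 |
|---|---|---|---|---|
| 1% | 4.6% (4–5%) | 2.6 | 9% (5–17%) | 4.2% |
| 2% | 8.5% (7–10%) | 4.8 | 12% (7–21%) | 7.5% |
| 5% | 18.6% (15–22%) | 10.4 | 17.5% (12–26%) | 15.3% |
| 10% | 32.1% (26–38%) | 18.0 | 24% (17–33%) | 24.5% |

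If the Safety Follow-up Visit falls in the TE period there are seven visits, and the central case rises to 1 − 0.7967 = 20.3%.

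**Where the excess comes from.** In the central case the tally stands 18.6 − 5 = 13.6 percentage points above the rate at a single visit. Counting only new-onset children takes off 18.6 − 15.3 = 3.3 points. The rest is accumulation over repeated visits. A by-visit table under the same assumptions would show about 5% (2.8 of 56) at baseline and about 5% at each later visit, which tells the reader that nothing has changed.

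**The case against.** The strongest reply is that the information is already there. The listing covers scheduled and unscheduled readings, and with about 56 children each flagged child can be traced back to baseline. The Part B by-visit blood-pressure counts already show the per-visit rate. Day 1 (Baseline) is a named vital-signs visit in SAP Table 12-2, and the table's note 1 says those visit names are used for reporting. This stands as mitigation: it would be wrong to infer that a reader has no way to tell new from old. But a listing leaves the reader to build the table by hand, and visit totals cannot do it. The baseline row is not stated either, and SAP 9.4 bases safety analyses on TE-period data, which start at the first dose.

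Three further readings are tempting, and the documents do not support them.
- *Blood pressure alone is treated this way.* Table 12-5 also uses absolute criteria for heart rate, QRS and one set of QTc limits, no ECG shift table is planned, and laboratory shifts cover selected parameters only.
- *These children are recorded as adverse events.* The tally is a descriptive threshold count. Protocol 13.1.1.2 ties AEs from vital signs to clinically significant worsening from baseline, and SAP 9.4.1 requires a TEAE to be new or worsened.
- *The thresholds should require a change from baseline.* That would lower the count, but it would also drop real out-of-range readings in children who start near a limit. An absolute screen is a defensible choice for descriptive paediatric safety.

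It is also fair to say that pre-existing excursions are the smaller part of the inflation, fewer than two children of 56 in the central case.

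**Conclusion.** The point holds as a limited reporting gap. The summary count mixes excursions present before dosing with new ones, in an uncontrolled study where vital signs are part of the Part B primary endpoint, and no planned table separates them. No inference is invalidated, since safety is descriptive.

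The gain from repair is modest. In the central case about one flagged child in six was already beyond the limit at baseline, and most of the remaining excess is repeated-visit accumulation, which only a by-visit table with a baseline row helps to interpret. These sizes rest on an assumed excursion rate, an assumed correlation and full attendance at six visits. The mixing itself does not depend on those figures.

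**What to change.** In SAP 9.4.4:
1. Add a shift table for SBP and for DBP, baseline category by worst TE-period category, with the high and low directions shown separately.
2. Beside each threshold count, report the count among children not beyond that limit at baseline. In the central case that is 15.3/95 = 16.1% of a denominator of about 53 (56 × 0.95).
3. State that the Part B by-visit blood-pressure threshold table includes the Day 1 (Baseline) row, so that each on-treatment rate can be read against it.

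Keep the absolute limits in Table 12-6 and add no change-from-baseline condition. The cost is SAP wording, one extra table and a slightly smaller denominator for the new-onset counts. No new data are needed.

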9.4.5 Pulse Oximetry

Part A and Part B

For the treatment-emergent pulse oximetry measurements, a summary of observed values and change from baseline values will be provided at each visit for the percent of oxygen saturation.

The number and percentage of subjects with shift change from baseline (normal/missing and low according to the reference range) to the lowest percent of oxygen saturation during the TE period will be summarized. The reference range for normal oxygen saturation is specified as >95%, and ≤95% for low oxygen saturation.

9.4.6 Ophthalmologic Examinations

Part A and Part B

The ophthalmologic examination results will be presented in individual subject data listings.

9.4.7 Physical Examination

[figure not shown]
[figure not shown]
Part A and Part B

[figure not shown]
Abnormal PE findings will be presented as an individual subject data listing only.

9.4.8 COVID-19 Impacted Visits

A listing containing subjects' visits impacted due to COVID-19 will be provided.

10 INTERIM AND DMC ANALYSES

10.1 Interim Analysis

Part A

No interim analysis is planned.

Part B

No interim analysis is planned at this moment; otherwise, SAP will be amended.

10.2 IDMC Analysis

Part A

No IDMC analysis is planned.

Part B

The DMC's objectives and operational details will be defined in a separate document (DMC Charter) which will be finalized before the first subject is screened in Part B of the study. The DMC's planned safety reviews of study data will be outlined in the DMC Charter and DMC Statistical Analysis Plan.

12 LIST OF APPENDICES

▪ Appendix A: Analysis Visit Windows for Safety and Efficacy Assessments

Table 12-1 Analysis Visit Windows for Safety and Efficacy Assessments in Part A			
Assessment	Visit¹	Target Study Day	Analysis Visit Window (in study days)^{2, 3, 4}
Safety Assessment			

 • Serum Chemistry • Hematology 	Day 1 (Baseline)	1	≤1 Pre-dose
	Day 8	8	[1, 12]
	Day 15	15	(12, 29]
	Safety Follow-up	Not applicable	Use nominal visit

 • Standard 12-lead ECG 	Day 1 (Baseline)	1	≤1 Pre-dose
	Day 2	2	[1, 9]
	Day 15 Pre-dose and Post-dose	Not applicable	Use nominal visit
	Safety Follow-up	Not applicable	Use nominal visit

 • Vital Signs 	Day 1 (Baseline)	1	≤1
	Day 2	2	[1, 5]
	Day 8	8	(5, 12]
	Day 15	15	(12, 29]
	Safety Follow-up	Not applicable	Use nominal visit

 • Coagulation 	Day 1 (Baseline)	1	≤1 Pre-dose
	Day 15	15	[1, 29]
Efficacy Assessment and Pharmacodynamic Assessment			

 • Spirometry 	Day 1 (Baseline)	1	≤1 Pre-dose
	Day 2	2	(1, 5]
	Day 8	8	(5, 12]
	Day 15	15	(12, 29]
	Safety Follow-up	Not applicable	>29

 • Sweat Chloride 	Day 1 (Baseline)	1	≤1 Pre-dose
	Day 15	15	(1, 29]

 • Weight, Height and BMI (and the corresponding z-scores, as applicable) 	Day 1 (Baseline)	1	≤1
	Day 15	15	(1, 29]
	Safety Follow-up	Not applicable	>29

Table 12-2 Analysis Visit Windows for Safety and Efficacy Assessments in Part B			
Assessment	Visit¹	Target Study Day	Analysis Visit Window (in study days)^{2, 3, 4}
Safety Assessment			
• Serum Chemistry	Day 1 (Baseline)	1	≤1 Pre-dose
	Day 15	15	[1, 22]
	Week 4	29	(22, 43]
	Week 8	57	(43, 71]
	Week 12	85	(71, 99]
	Week 16	113	(99, 127]
	Week 20	141	(127, 155]
	Week 24	169	(155, 183]
	Safety Follow-up	Not applicable	Use nominal visit
• Hematology	Day 1 (Baseline)	1	≤1 Pre-dose
	Day 15	15	[1, 22]
	Week 4	29	(22, 43]
	Week 8	57	(43, 71]
	Week 12	85	(71, 99]
	Week 16	113	(99, 141]
	Week 24	169	(141, 183]
		Safety Follow-up	Not applicable
• Vital Signs (excluding weight, height, and BMI)	Day 1 (Baseline)	1	≤1
	Day 15	15	[1, 22]
	Week 4	29	(22, 43]
	Week 8	57	(43, 71]
	Week 12	85	(71, 99]
	Week 16	113	(99, 141]
	Week 24	169	(141, 183]
		Safety Follow-up	Not applicable
• Standard 12-lead ECG	Day 1 (Baseline)	1	≤1 Pre-dose
	Day 15	15	[1, 50]
	Week 12	85	(50, 99]
	Week 16	113	(99, 141]
	Week 24	169	(141, 183]
		Safety Follow-up	Not applicable
• Coagulation	Day 1 (Baseline)	1	≤1 Pre-dose
	Week 24	169	[1, 183]
	Safety Follow-up	Not applicable	Use nominal visit
Efficacy Assessment and Pharmacodynamic Assessment			
• Spirometry	Day 1 (Baseline)	1	≤1 Pre-dose
	Day 15	15	(1, 22]
	Week 4	29	(22, 43]
	Week 8	57	(43, 71]
	Week 12	85	(71, 99]
	Week 16	113	(99, 141]
	Week 24	169	(141, 183]
		Safety Follow-up	Not applicable

Table 12-2 Analysis Visit Windows for Safety and Efficacy Assessments in Part B			
Assessment	Visit¹	Target Study Day	Analysis Visit Window (in study days)^{2, 3, 4}

 Weight, Height and BMI (and the corresponding z-scores) 	Day 1 (Baseline)	1	≤1
	Day 15	15	(1, 22]
	Week 4	29	(22, 43]
	Week 8	57	(43, 71]
	Week 12	85	(71, 99]
	Week 16	113	(99, 141]
	Week 24	169	(141, 183]
	Safety Follow-up	Not applicable	>183

 Modified Facial Hedonic Scale 	Day 1	1	≤1
	Day 15	15	(1, 22]
	Week 4	29	(22, 43]
	Week 8	57	(43, 71]
	Week 12	85	(71, 99]
	Week 16	113	(99, 141]
	Week 24	169	(141, 183]
	Safety Follow-up	Not applicable	>183

 CFQ-R 	Day 1 (Baseline)	1	≤1
	Week 4	29	(1, 43]
	Week 8	57	(43, 71]
	Week 12	85	(71, 99]
	Week 16	113	(99, 141]
	Week 24	169	(141, 183]
	Safety Follow-up	Not applicable	>183

 Sweat Chloride Lung Clearance Index 	Day 1 (Baseline)	1	≤1 Pre-dose
	Day 15	15	(1, 22]
	Week 4	29	(22, 57]
	Week 12	85	(57, 127]
	Week 24	169	(127, 183]

Notes:

¹ Visit name for analysis purpose is used to report data in tables and figures.

² The analysis visit windows will be applied using the following rules for both scheduled and unscheduled visits:

- If no numerical measurement is available within a visit window, the measurement will be considered missing for the visit.
- If there is more than 1 numerical measurement available within a visit window, use the following rules:
 - The measurement closest to the target day will be used; or
 - If there are multiple measurements with the same distance from the target day, the latest measurement will be used. If the latest measurement cannot be determined, then unscheduled visit will be selected

³ For measurements collected on the date of first dose of study drug, if it cannot be determined whether the measurement is before or after the first dose:

- a. Scheduled measurement will be treated as pre-dose observation.
- b. Unscheduled measurement will be treated as post-dose observation.

⁴ For safety assessment, Safety Follow-up analysis visit will be based on nominal Safety Follow-up visit. If a subject doesn't have a nominal Safety Follow-up visit but has an ETT visit with study day >29 for Part A and >183 for Part B, then the ETT visit will be mapped into Safety Follow-up analysis visit.

⁵ For efficacy analysis of Part B, if there are assessments with study days > 183, the nominal Safety Follow-up visit will be mapped to the Safety Follow-up visit. If there is only ETT assessment with study day > 183, the ETT visit will be mapped to the Safety Follow-up visit.

Derived Variables:

1. Age (in years) at first dose date and nominal visit (for demographics, listing and the calculation of [percent] predicted spirometry variables):

Obtain the age at informed consent/assent (in days) in "yy, mm" format (e.g., 24 years, 6 months) from the Vital Signs (VS) page at the Screening Visit, and add 0.5 month to convert to days.

Obtain the informed consent/assent date.

Then age (in years) at first dose or nominal visit = [(first dose date or nominal visit date – informed consent/assent date) in days + age at informed consent/assent (in days)]/365.25.

2. Age (in months) at nominal visit (for use in calculation of BMI, weight z-score and height z-score, as applicable):

Obtain the age at informed consent/assent (in months) in "yy, mm" format (e.g., 24 years, 6 months) from Vital Signs (VS) page at the Screening Visit.

Obtain the informed consent/assent date.

Then age (in months) at nominal visit = integer part of {[age at informed consent/assent (in months) + 0.5 + diff (first dose date or nominal visit date, informed consent/assent date) in months]} + 0.5.

3. Missing first dose date or last dose date

If the first dose date is missing, use Day 1 visit date to impute.

If the last dose date is missing or partial date is reported, the last dose date will be imputed based on, in descending order priority, the Early Treatment Termination (ETT) visit date, last visit date before the Safety Follow-up, or the last study drug administration date from EX SDTM domain, as appropriate. The imputation algorithm will ensure the imputed last dose date does not exceed the study participation end date.

4. Sweat Chloride:

Non-missing sweat chloride concentrations from the left arm and right arm with assessment end date/time for a given arm up to 30 minutes after first dose time in treatment period will be considered for baseline.

5. Electrocardiogram:

Baseline will be defined as the most recent non-missing measurement (or the average of triplicate measurements, if the most recent non-missing measurement is obtained in triplicate), before the first dose of study drug in the Treatment Period. If multiple ECG measurements are obtained on the same calendar day during the TE period,

- o For summary purpose, the calculated average ECG will be used as the ECG value on that day (except for Day 15 visit in Part A);
- o For threshold analysis purpose, all reported ECG values will be used.

▪ **Appendix B: Imputation Rules for Missing Prior/Concomitant Medication Dates**

Imputation rules for missing or partial medication start/stop dates are defined below:

1. Missing or partial medication start date:
 - a. If only DAY is missing, use the first day of the month.
 - b. If DAY and Month are both missing, use the first day of the year.
 - c. If DAY, Month and Year are all missing, use a date before the first dose date (in practical, use Jan. 01, 2000 to impute).
2. Missing or partial medication stop date:
 - a. If only DAY is missing, use the last day of the month.
 - b. If DAY and Month are both missing, use the last day of the year.
 - c. If DAY, Month and year are all missing, assign ‘continuing’ status to stop date (in practical, use Dec. 31, 2050 to impute).

In summary, the prior, concomitant, or post categorization of a medication is described below.

Table 12-3 Prior, Concomitant, and Post Categorization of a Medication

Medication Start Date	Medication Stop Date		
	< First Dose Date of Study Drug	≥ First Dose Date and ≤ End Date of TE Period	> End Date of TE Period
< First dose date of study drug	P	PC	PCA
≥ First dose date and ≤ End date of TE period	-	C	CA
> End date of TE period	-	-	A

P: Prior; C: Concomitant; A: Post

Imputation rules for missing and/or partial dates of non-pharmacological treatment/procedure will follow the same imputation rule.

▪ **Appendix C: Details of GLI Equations for Calculating ppFEV₁**

Percent predicted values will be calculated for parameters of FEV₁, FVC, FEV₁/FVC, and FEF_{25%-75%} using the Quanjer GLI-2012 Regression Equations and Lookup Tables.

The regression equations and lookup tables required to implement the Quanjer GLI-2012 predicted values are available in:

Philip H. Quanjer, Sanja Stanojevic, Tim J. Cole, Janet Stocks. Quanjer GLI-2012 Regression Equation and Lookup Tables (Version 7 April 2013). Global Lung Function Initiative. [online] Available at: <http://www.ers-education.org/home/browse-all-content.aspx?idParent=138978> [Accessed Mar 26, 2018].

The instructions and tools on how to implement the Quanjer GLI-2012 equations are:

Philip H. Quanjer, Sanja Stanojevic, Tim J. Cole, Janet Stocks. Implementing GLI-2012 regression equations (Version 19 July 2015). Global Lung Function Initiative. [online] Available at: <http://www.ers-education.org/home/browse-all-content.aspx?idParent=138979> [Accessed Mar 26, 2018].

Sanja Stanojevic. GLI-2012 - SAS Macro (Version 2, 7 April 2013). Global Lung Function Initiative. [online] Available at: <http://www.ers-education.org/home/browse-all-content.aspx?idParent=138988> [Accessed Mar 26, 2018].

Data handling rule for spirometry is as follows:

- Input age and height with at least 2 decimal place
- Height collected at the respective visit should be used; if the height at the respective visit is not available, the last non-missing record will be used.
- For race, map the CRF reported Black or African American to Black, all other races in CRF (except White) are mapped to 'other'; multiple checks for race in CRF are also mapped to 'other'; white is a reference race in the equations and assumes 0 values for all race coefficients in the GLI equations.

▪ **Appendix D: Imputation Rules for Missing AE Dates**

Imputation rules for missing or partial AE start date are defined below. If the imputed AE start date is before the study informed consent/assent date, the AE start date will be imputed using the study informed consent/assent date.

• **If only Day of AE start date is missing:**

- If the full (or partial) AE end date is NOT before the first dose date of the Treatment Period or AE end date is missing, then
 - if AE start year and month are equal to the month and year of first dose date of the Treatment Period, then impute the AE start day as the day of first dose date of the Treatment Period;
 - else impute the AE start day as 1.
- else impute the AE start day as 1.

Compare the imputed AE start date with TE period to determine whether the AE is pretreatment AE, TEAE or post-treatment AE.

• **If Day and Month of AE start date are missing:**

- If the full (or partial) AE end date is NOT before the first dose date of the Treatment Period or AE end date is missing, then
 - if AE start year is equal to the year of first dose date of the Treatment Period, then impute the AE start month and day as the month and day of first dose date of the Treatment Period;
 - else impute the AE start month as January and day as 1.
- else impute the AE start month as January and day as 1.

Compare the imputed AE start date with TE period to determine whether the AE is pretreatment AE, TEAE or post-treatment AE.

• **If Year of AE start date is missing:**

If the year of AE start is missing or AE start date is completely missing then query site and

- If the full (or partial) AE end date is NOT before the first dose date of the Treatment Period or AE end date is missing, then impute the AE start date as the first dose date of the Treatment Period;
- else impute the AE start date as the informed consent/assent date.

Imputation rules for partial AE end date are defined below:

- Impute the AE end date as min (the last day of the month, end of study participation) if day is missing, or min (Dec, end of study participation) if month is missing.

▪ **Appendix E: Criteria for Threshold Analysis**

Table 12-4 Threshold Analysis Criteria for Laboratory Tests (as applicable)

Parameter	Threshold Analysis	Comments
Clinical Chemistry (LFT)		
ALT	>ULN - ≤3xULN >3x - ≤5xULN >5x - ≤8xULN >8x - ≤20xULN >20xULN	FDA DILI Guidance Jul 2009.
AST	>ULN - ≤3xULN >3x - ≤5xULN >5x - ≤8xULN >8x - ≤20xULN >20xULN	FDA DILI Guidance Jul 2009.
ALT or AST	(ALT>ULN - ≤ 3xULN) or (AST>ULN - ≤3xULN) (ALT>3x - ≤5xULN) or (AST>3x - ≤5xULN) (ALT>5x - ≤8xULN) or (AST>5x - ≤8xULN) (ALT>8x - ≤20xULN) or (AST>8x - ≤20xULN) ALT>20xULN or AST>20xULN	FDA DILI Guidance
Alkaline Phosphatase	>ULN - ≤1.5xULN >1.5x - ≤2.5xULN >2.5x - ≤5xULN >5x - ≤20xULN >20xULN	FDA DILI Guidance Jul 2009.
Total Bilirubin	>ULN - ≤1.5xULN >1.5x - ≤2xULN >2x - ≤3xULN >3x - ≤10xULN >10xULN	FDA DILI Guidance Jul 2009.
Direct Bilirubin	>ULN - ≤1.5xULN >1.5x - ≤2xULN >2x - ≤3xULN >3x - ≤10xULN >10xULN	FDA DILI Guidance Jul 2009.
Indirect Bilirubin	>ULN - ≤1.5xULN >1.5x - ≤2xULN >2x - ≤3xULN >3x - ≤10xULN >10xULN	FDA DILI Guidance Jul 2009.

Table 12-4 Threshold Analysis Criteria for Laboratory Tests (as applicable)

Parameter	Threshold Analysis	Comments
ALT and Total Bilirubin	ALT>3xULN and TBILI>2xULN	FDA DILI Guidance Jul 2009.
AST and Total Bilirubin	AST>3xULN and TBILI>2xULN	FDA DILI Guidance Jul 2009.
(ALT or AST) and Total Bilirubin	(ALT>3xULN or AST>3xULN) and TBILI>2xULN	FDA DILI Guidance Jul 2009.
GGT	>ULN - ≤2.5xULN >2.5x - ≤5xULN >5x - ≤20xULN >20xULN	CTCAE grade 1-4
Clinical Chemistry (NON-LFT)		
Albumin	<LLN - ≥30 g/L <30 - ≥20 g/L <20 g/L	CTCAE grade 1-3
Amylase	>ULN - ≤1.5xULN >1.5x - ≤2xULN >2x - ≤5xULN >5xULN	Criteria based upon CTCAE
Creatinine	>ULN - ≤1.5xULN >1.5x - ≤3xULN >3x - ≤6xULN >6xULN	CTCAE grades 1-4
Lipase	>ULN - ≤1.5xULN >1.5x - ≤2xULN >2x - ≤5xULN >5xULN	Criteria based upon CTCAE
Total protein	<LLN >ULN	No CTCAE
Creatine kinase	>ULN - ≤2.5xULN >2.5x - ≤5xULN >5x - ≤10xULN >10xULN	CTCAE grades 1-4
Hematology		
Hemoglobin	Hgb decreased (anemia) <LLN - ≥100 g/L <100 - ≥80 g/L <80 g/L Hgb increased >ULN - ≤20 g/L above ULN >20 g/L above ULN - ≤40 g/L above ULN >40 g/L above ULN	CTCAE grade 1-3 CTCAE grade 1-3

Table 12-4 Threshold Analysis Criteria for Laboratory Tests (as applicable)

Parameter	Threshold Analysis	Comments
Platelets	Platelet decreased <LLN - $\geq 75 \times 10^9 /L$ <75 - $\geq 50 \times 10^9 /L$ <50 - $\geq 25 \times 10^9 /L$ <25 $\times 10^9 /L$	CTCAE grade 1-4
	Platelet increased >ULN	No CTCAE available
Reticulocytes/Erythrocytes (%)	<LLN >ULN	No CTCAE
Coagulation		
Activated partial thromboplastin time (PTT)	>ULN - $\leq 1.5 \times ULN$ >1.5 - $\leq 2.5 \times ULN$ >2.5 $\times ULN$	CTCAE grade 1-3
Prothrombin time (PT) International Normalized Ratio (INR)	>ULN - $\leq 1.5 \times ULN$ >1.5 - $\leq 2.5 \times ULN$ >2.5 $\times ULN$	CTCAE grade 1-3

Table 12-5 Threshold Analysis Criteria for ECGs

Parameter	Threshold Analysis	Comments
HR	Bradycardia ≤ 50 bpm	
	Tachycardia ≥ 140 bpm	
PR	≥ 220 ms and increase from baseline ≥ 20 ms	
QRS	≥ 120 ms	
QTc	Absolute values (ms) >450 ms (Male); >470 ms (Female) ≥ 500 ms	To be applied to any kind of QT correction formula.
	Increase from baseline Increase from baseline 30-60 ms Increase from baseline >60 ms	

Table 12-6 Threshold Analysis Criteria for Vital Signs

Parameter	Threshold Analysis	Comments
SBP	>120 mmHg	
	<70 mmHg	
DBP	>80 mmHg	
	<50 mmHg	

Table 12-6 Threshold Analysis Criteria for Vital Signs

Parameter	Threshold Analysis	Comments
Weight	Weight gain ≥5% increase from baseline	
	Weight loss ≥5% decrease from baseline
